Appendix B: Schedule of Procedures/Evaluations45
Appendix C: Lab Processing Flow Sheet/Template for Specimen Collection47

NIH Approved 08/18/2016

List of Abbreviations

AE	Adverse Event/Adverse Experience
CCHMC	Cincinnati Children's Hospital Medical Center
CFR	Code of Federal Regulations
CHCO	Children's Hospital Colorado
CHOP	Children's Hospital of Philadelphia
COI	Conflict of Interest
COM	Clinical Outcome Measure
CRF	Case Report Form
CRO	Contract Research Organization
CRPC	Central Review Pathology Committee
DHHS	Department of Health and Human Services
EC	Eosinophilic Colitis
EDP	EoE Diagnostic Panel
EG	Eosinophilic Gastritis
EoE	Eosinophilic Esophagitis
FWA	Federal Wide Assurance
GCP	Good Clinical Practice
GI	Gastrointestinal
HIPAA	Health Insurance Portability and Accountability Act
HPF	High Power Field
HUP	Hospital of University of Pennsylvania
ICF	Informed Consent Form
IRB	Institutional Review Board
ISM	Independent Safety Monitor
IU	Indiana University School of Medicine/IU Health
LCH	Lurie Children's Hospital
MOP/MOO	Manual of Procedures/Manual of Operations
N	Number (typically refers to participants)
NIAID	National Institute of Allergy and Infectious Diseases
NIH	National Institutes of Health
NW	Northwestern University
OHRP	Office for Human Research Protections

OHSR	Office of Human Subjects Research
PHI	Protected Health Information
PI	Principal Investigator
PPI	Proton Pump Inhibitor
PRO	Patient Reported Outcomes
QA	Quality Assurance
QC	Quality Control
RCHSPB	Regulatory Compliance and Human Subjects Protection Branch
RCHSPP	Regulatory Compliance and Human Subjects Protection Program
RHC	Riley Hospital for Children
SAE	Serious Adverse Event/Serious Adverse Experience
SMC	Safety Monitoring Committee
SOP	Standard Operating Procedure
TMC	Tufts Medical Center
UCSD	University of California, San Diego
UNC	University of North Carolina

NIH Approved 08/18/2016

Protocol Summary

Full Title:	A Prospective, Multicenter Study to Compare and Validate Endoscopic, Histologic, Molecular, and Patient-reported Outcomes in Pediatric and Adult Patients with Eosinophilic Esophagitis (EoE), Gastritis (EG), and Colitis (EC)
Short Title:	OMEGA
Conducted by:	Consortium of Eosinophilic Gastrointestinal Disease Researchers (CEGIR)
Sample Size:	N= 600 EoE, 300 EG, and 150 EC patients (total for all participating sites), 150 non EGID for Normal controls
Accrual Ceiling:	This study plans to continue enrollment for the duration of funding.
Study Population:	
Males or Females ≥ 3 years of age; presence of symptoms including but not limited to:
 
• EoE- abdominal pain, vomiting, heartburn, feeding/eating problems, dysphagia, food impaction• EG- abdominal pain, vomiting• EC- bloody/non bloody diarrhea, tenesmus, abdominal pain 
Mucosal eosinophilia:
 
• EoE- ≥ 15 eosinophils/HPF• EG- ≥ 30 eosinophils/HPF in 5 HPFs• EC- ≥ 65 eosinophils/HPF
Accrual Period:	The projected date of enrollment for this study is January 2015. We will accrue subjects for 5 years or longer if funding is renewed.
Study Design:	Prospective longitudinal cohort study. This study is observational in nature and no treatments or products are being studied.
Study Duration:	Subjects enrolled and followed for the duration of funding (5 years) and longer if funding is renewed.
Primary Objective:	
Specific Aim 1- Determine the correlation of EoE, EG, and EC clinical outcome measures (COMs) with mucosal eosinophilia.
 
Primary Objective-To perform a prospective, multicenter, pediatric and adult longitudinal study to determine the correlation of COMs

(PROs, QoL and endoscopy) with the established biomarker of peak mucosal eosinophil count (Phase 1).

Specific Aim 2- Determine the correlation of the molecular profile for EoE, EG, and EC with clinical outcome measures (COMs) and mucosal eosinophilia.

Primary Objective-To perform a prospective, multicenter, pediatric and adult exploratory study to compare the transcriptomes (EoE-transcriptome, EG-transcriptome and EC-transcriptome) with their respective peak mucosal eosinophil counts and respective COMs generated in Aim 1.

Secondary Objectives: Specific Aim 1

Secondary Objective-To determine how the EoE, EG and EC COMs and tissue histology change over time in order to determine a better understanding of the natural history of the disease and response to therapy. (Phase 2)

Exploratory Objectives: Specific Aim 2

Secondary Objective- To perform an exploratory study to compare the three transcriptomes to each other in order to identify patterns of similarity and differences in order to understand the etiological relationship of these diseases and potential therapeutic strategies moving forward.

Creation of DNA repository

Exploratory Objective- To isolate and study some of the proteins, RNA, and DNA (the material contained in genes) from the blood such as the level of eosinophil attraction proteins (eotaxins) and eosinophil growth factors (such as interleukin 5). DNA will be banked at CCHMC for future studies including genome wide association analyses (GWAS), candidate gene analyses and sequencing. Results will be deposited into dbGAP if required by NIH.

1 Key Roles

PROTOCOL CHAIR

[name]
Professor of Pediatrics
University of Colorado School of Medicine/Children's
Hospital Colorado
[name]
[name]
[contact]
[contact]
Email: [contact]

CO-PROTOCOL CHAIR

[name], PhD
Division of Allergy and Immunology
Associate Professor, Pediatrics and Medicine
Director, Eosinophilic Gastrointestinal Disorders Clinic
University of California, San Diego
Rady Children's Hospital, San Diego
[name]
[name]
[contact]
[contact]
Email: [contact]

NIAID MEDICAL MONITOR

[name] [name]
Division of Allergy, Immunology, and Transplantation –
NIAID/NIH
[name]
[name]
[contact] (office)
[contact]
E-mail: [contact]

NIAID PROJECT MANAGER

[name], RNP, MSN, CCRP
Division of Allergy, Immunology, and Transplantation
– NIAID/NIH
[name]
[name]
[contact]
E-mail: [contact]

**DATA MANAGEMENT AND COORDINATING CENTER
PRINCIPAL INVESTIGATOR**

[name]
[name]
[name]
[contact]
Email: [contact]

2 Background Information and Scientific Rationale

2.1 Background Information

2.1.1 Summary of Relevant Studies

Over the course of the last decade, investigators have taken a stepwise approach to define the diagnostic criteria of EoE and to develop metrics for assessing disease activity. These approaches, so far limited to EoE, have included reaching a consensus about the diagnostic threshold of tissue eosinophil levels, as well as the identification of tissue based transcript signatures that differentiate EoE from control individuals and correlate with disease activity and pathological components, and finally the development of outcome metrics that quantify tissue, endoscopic and clinical parameters. A summary of some of these developments is presented below:

1. *Consensus Recommendation*- the first Consensus Recommendations published in *Gastroenterology*¹ as well as second and third revisions published in *Journal of Allergy and Clinical Immunology*² and *American Journal of Gastroenterology*³, respectively. Each of these peer-reviewed revisions has utilized newly published data to continually revise and reshape clinically relevant and scientifically sound recommendations for the practitioner and researcher.
2. *Clinical Outcome Measure (COM) tools*- investigators have developed COMs. These metrics include the Pediatric EoE Symptom Score (PEESS)⁴, Pediatric Quality of Life (PedsQL™) EoE module⁵, EoE Symptom Activity Index (EESAI), REGID Provider Questionnaire and endoscopic scoring system (EREFS)⁶.
3. *Molecular Criteria for Disease Diagnosis*- Investigators have demonstrated that a panel of EoE related genes (EoE-transcriptome) has high sensitivity and specificity for diagnosing and monitoring EoE⁷. Importantly, the results of this gene panel align when assessed using either fresh tissue or formalin fixed paraffin embedded (FFPE) specimens, which significantly increases its applicability.
4. *Correlation of transcriptome with COMs*- Based on the EoE-transcriptome and the PEESS Patient Reported Outcome (PRO), investigators have preliminarily correlated increased immunoinflammatory gene expression and the cardinal clinical symptom of dysphagia in pediatric EoE (unpublished data). For example, as discussed below, genes involved in inflammation, including those that encode for eosinophil and mast cell products and interleukin receptors, correlate with dysphagia.

2.1.2 Summary of Epidemiological Data

Diverse clinical presentations, unknown pathogenesis and lack of treatments distinguish these rare diseases- Eosinophilic esophagitis (EoE), gastritis (EG) and colitis (EC) are each considered a rare disease on the basis of the estimated prevalence of less than 200,000 each in the US^{2, 8-10}. Each constitutes a chronic inflammatory disease characterized by gastrointestinal (GI) symptoms and dense mucosal eosinophilia. These diseases share the histologic finding of robust mucosal eosinophilia and have variable presentations. For example, while EoE is characterized by symptoms of feeding difficulties and vomiting in young children and food impactions and dysphagia in teenagers and adults, EG patients have upper abdominal pain, nausea and vomiting and EC patients present with diarrhea, hematochezia and lower abdominal

and rectal pain¹¹⁻¹³. To date, the diagnosis of each of these diseases rests on the finding of dense mucosal eosinophilia in the proper clinical setting when all other causes of mucosal eosinophilia are ruled out. Currently, little is known regarding the natural history and pathophysiological mechanisms, especially for EG and EC, and FDA approved drugs do not exist for any of these diseases.

Variability in correlation of mucosal eosinophilia with GI symptoms- Elevated eosinophil levels are required for diagnosis of these diseases and it has generally been accepted that eosinophil counts correlate with disease activity. However, few studies have directly addressed whether eosinophils are the best histological component that correlates with clinical symptoms and these studies have been primarily limited to EoE¹⁴. Proving the fundamental assumption that tissue eosinophil counts correlate with disease activity will indeed be a major focus of the proposed study.

A number of issues are likely contributing to the uncertainty about the best tissue features to monitor for correlation with clinical symptoms. These include 1) lack of validated metrics to assess whether symptoms or PROs align with tissue histology measures; 2) lack of prospective, randomized, placebo controlled trials that have utilized the same primary outcome variables; 3) lack of studies that have cohort sizes that are truly powered to find correlations between symptoms and tissue histology elements; 4) the intermittent nature of symptoms and the ability of patients to institute behavioral and lifestyle changes to compensate for their symptoms¹⁵; and 5) inconsistent measurements of tissue eosinophil counts in various studies¹⁶.

In this study, we will overcome many of the limitations of prior studies by (1) utilizing a series of uniform clinical outcome measures (COMs); (2) conducting a large multi-site prospective trial with well-defined entry criteria, and (3) standardizing the way in which tissue eosinophil counts and other histological features are measured.

Complexity of tissue eosinophil counts as diagnostic feature of EG and EC-The normal esophagus is void of mucosal eosinophils¹⁷. As such, the histological assessment of EoE is relatively straightforward. In contrast, the diagnosis of EG and EC are particularly complex as eosinophils are normal resident cells in the gastrointestinal mucosa¹⁷⁻¹⁹. For all of these diseases, increased mucosal eosinophils are not pathognomonic for EoE, EG, or EC as they can be seen in other diseases including reflux esophagitis, food allergy, inflammatory bowel diseases and infections²⁰. As such, definitions of key clinical and histological features, especially for patients with EG and EC are urgently needed. Currently, based on limited data and clinical experiences, it has been proposed that the diagnostic criteria for EG and EC includes the histological finding of at least twice the normal peak number of eosinophils per high power field (eos/hpf) reported in different regions of the non-diseased stomach and/or colon²¹⁻²³. During the course of studies defined herein, we seek to advance the field by determining the relationships between COMs and mucosal eosinophilia that will ultimately assist in developing diagnostic criteria, understanding mechanisms, and identifying endpoints for treatment efficacy.

Lack of understanding of pathophysiology- Pathophysiological mechanisms defining EoE have made great strides in the last decade^{24, 25}. For instance, a number of studies identified dysregulation of the allergic arm of the immune system in the pathogenesis of EoE²⁶. This etiology is supported by the reversibility of EoE following dietary avoidance of specific foods²⁷, the reoccurrence of EoE upon re-introduction of the removed foods²⁸, the induction of the disease in mice by exposure to both food and aero-allergens²⁹, and genome-wide transcriptome analysis of esophageal tissue that implicated an interplay between the innate and adaptive immune responses³⁰⁻³². EoE has a strong hereditary component with a large sibling risk ratio ($\lambda_s \sim 80$)³².

Early genetic analyses have identified susceptibility loci in the regions that contain candidate genes expressed in epithelial cells and strongly implicated in antigen recognition (*TSLP*, thymic stromal lymphopoietin) and inflammatory cell recruitment / activation (*CCL26*, eotaxin-3)^{26, 30, 31}. The Th2 cytokine IL-13 programs transcription of key EoE-related genes and pathways and TGFβ1 has been proposed to be a regulator of EoE pathogenesis^{33, 34}. In contrast, our understanding of EG and EC is in its nascency with current murine model studies that suggest roles for eosinophil associated cytokines eotaxin-1 and IL-5³⁵. Thus, while early evidence suggests that these diseases occur as a result of immune dysfunction, specific targets and biomarkers remain to be fully recognized.

2.2 Rationale

A number of issues are likely contributing to the uncertainty about the best tissue features to monitor for correlation with clinical symptoms. These include 1) lack of validated metrics to assess whether symptoms or PROs align with tissue histology measures; 2) lack of prospective, randomized, placebo controlled trials that have utilized the same primary outcome variables; 3) lack of studies that have cohort sizes that are truly powered to find correlations between symptoms and tissue histology elements; 4) the intermittent nature of symptoms and the ability of patients to institute behavioral and lifestyle changes to compensate for their symptoms⁶; and 5) inconsistent measurements of tissue eosinophil counts in various studies¹⁶.

In this study, we will overcome many of the limitations of prior studies by utilizing 1) a series of uniform clinical outcome measures (COMs); 2) conducting a multi-site prospective trial with well-defined entry criteria; and 3) standardizing measurements of tissue eosinophilia and other histological features.

3 Study Objectives

3.1 Primary Objective

Specific Aim 1- Determine the correlation of EoE, EG, and EC clinical outcome measures (COMs) with mucosal eosinophilia.

Primary Objective-To perform a prospective, multicenter, pediatric and adult longitudinal study to determine the correlation of COMs (PROs, QoL and endoscopy) with the established biomarker of peak mucosal eosinophil count (Phase 1).

Hypotheses: The overriding hypothesis of this aim is that clinical outcome measures (COMs) will correlate with the standard biomarker of mucosal eosinophilia in subjects with EoE, EG, and EC. In addition, we will test a series of other hypotheses to help determine phenotypes associated with EoE, EG and EC. The overall aim of these studies will be to measure clinical features of pediatric and adult EoE, EG, and EC in a cross sectional and longitudinal study and correlate these findings with the standard biomarker, mucosal eosinophilia. Clinical endpoints include pediatric and adult specific COMs such as patient-reported outcomes (PROs), quality-of-life (QoL) scales, endoscopic scores, and the histological endpoint peak will be mucosal eosinophil count in the respective organ (EoE-esophagus, EG-stomach, EC-colon).

Specific Aim 2- Determine the correlation of the molecular profile for EoE, EG, and EC with clinical outcome measures (COMs) and mucosal eosinophilia.

August 8, 2016

Primary Objective-To perform a prospective, multicenter, pediatric and adult exploratory study to compare the transcriptomes (EoE-transcriptome, EG-transcriptome and EC-transcriptome) with their respective peak mucosal eosinophil counts and respective COMs generated in Aim 1.

Hypothesis: We hypothesize that there is a disease specific mRNA expression profile in EoE, EG and EC that will associate with tissue eosinophil counts and COMs.

3.2 Secondary Objectives

Specific Aim 1

Secondary Objective-To determine how the EoE, EG and EC COMs and tissue histology change over time in order to determine a better understanding of the natural history of the disease and response to therapy. (Phase 2)

3.3 Exploratory Objectives

Specific Aim 2

Secondary Objective- To perform an exploratory study to compare the three transcriptomes to each other in order to identify patterns of similarity and differences in order to understand the etiological relationship of these diseases and potential therapeutic strategies moving forward.

Creation of DNA repository

Exploratory Objective- To isolate and study some of the proteins, RNA, and DNA (the material contained in genes) from the blood/saliva such as the level of eosinophil attraction proteins (eotaxins) and eosinophil growth factors (such as interleukin 5). We will bank the DNA for future studies including genome wide association analyses, candidate gene analyses and sequencing. Results will be deposited into dbGAP if required by NIH.

3.4 Substudy Objectives

For a subset of 30 subjects, the histology scoring tool will be tested for inter- and intra-observer reliability at baseline and end of treatment for acceptable variability.

3.5 Substudy Objectives

For a subset of 144 to 150 subjects we will conduct a prospective, observational study that will quantitatively characterize the microbiome of pediatric and adult subjects with Eosinophilic Esophagitis (EoE), Eosinophilic Gastritis (EG), and Eosinophilic Colitis (EC) along with a group of normal adult and pediatric controls, by characterizing alpha and beta diversity at the taxonomic level within and between these groups.

4 Study Design

4.1 Description of the Study Design

Specific Aim 1: Primary Objective (Phase 1)-We will conduct a prospective, observational study that will measure COMs and peak mucosal eosinophilia in pediatric and adult subjects with EoE, EG and EC. Subjects will be recruited by investigators located at multiple academic and research medical centers. Subjects will be enrolled who have a confirmed diagnosis of EoE, EG or EC regardless of

their treatment status, as we are interested in the relationship between mucosal inflammation, whether present or not, with the COMs.

Three groups of patients will be recruited; 1.) patients with an established diagnosis of EoE, EG or EC 2.) patients who have a new diagnosis of EoE, EG or EC and 3) healthy controls that are having endoscopy and/or colonoscopy (this group is for the mechanistic microbiome study). The second group will be enrolled within 4 weeks of the diagnostic endoscopy and prior to any treatments for their disease. Recruited patients will then 1.) sign informed consent, 2.) undergo standard of care (SOC) evaluation to capture defined clinical data, 3.) complete questionnaires, and 4.) analysis of their formalin-fixed, paraffin-embedded (FFPE) esophageal, gastric, or colonic biopsy (obtained as part of SOC) to measure peak eosinophil count and associated features. At the time of SOC endoscopy, subjects who have consented to have research biopsies collected will provide two to four additional biopsies for RNA and microbiome analysis (this will be repeated at each SOC endoscopy during the course of the study). At the time of the SOC endoscopy post enrollment (microbiome sub-study participants are not in study after the first SOC procedure is completed), subjects who have consented to donate blood/saliva/stool for this study will provide 10-15 mls of blood and/or 2 ml of saliva for DNA analysis and stool for storage and for microbiome analysis (see sub studies). At the time of endoscopy, one photograph image will be captured from the site of the research biopsies.

Correlation of COMs with peak eosinophil counts will lead to development of an understanding of optimal COM to measure disease activity. If an endoscopy is to be scheduled, the endoscopic score will be assigned at the time of the procedure. If the endoscopy has been already completed, the score will be performed on the recorded video/pictures as described below. Instructions and administering the COMs will be coordinated at each enrollment site.

Creation of DNA repository

Exploratory Objective- Subjects who consent to donate blood/saliva/ stool for this study will have their sample used to isolate and study some of the proteins, RNA, and DNA (the material contained in genes) from the blood such as the level of eosinophil attraction proteins (eotaxins) and eosinophil growth factors (such as interleukin 5). DNA will be banked at CCHMC for future studies including genome wide association analyses, candidate gene analyses and sequencing. Results will be deposited into dbGAP if required by NIH. Stool will be stored and used for studies not limited to assessment of microbiome.

Specific Aim 1: Secondary Objective (Phase 2)- In Phase 2 of this study, subjects enrolled in Phase 1 will continue to be followed and assessed at each of the following time points: 1.) annually, 2.) at the time of any change in SOC treatment and 3.) at the time of any endoscopic procedure. In scenarios 1, or 2, only PRO and QoL COMs will be completed, and in scenario 3, all COMs and histological analysis will be analyzed. All patients will be undergoing SOC during this time; SOC treatment will be the choice of the attending physician and may include systemic or topical steroids, diet, or immunosuppression. This is not an interventional study and thus *treatment will be monitored, but not prescribed* as a part of this protocol. This is a natural history study, and since SOC *maintenance* treatments and paradigms do not yet exist, we will only monitor COMs and histology over time and not dictate treatments. We have taken this approach for several reasons including the capture of “real world” data such that study findings are broadly applicable to the EoE, EG, and EC populations at large, to allow entry of the largest cohort of subjects independent of therapeutic intervention, and to better understand patient adherence to a prescribed therapeutic regimen as it relates to disease course.

Specific Aim 2: Primary Objective- We hypothesize that there will be largely unique gene profiles in each disease. We will utilize well characterized EoE, EG, and EC subjects and control subjects for gene expression analysis. We will perform genome-wide screening in the EG and EC populations since it is not clear what the gene expression profile is in these diseases. The EoE genome wide

expression data is already well identified so we will not repeat this analysis on the esophageal samples, at least initially. Our first objective will be to identify disease specific transcript profiles that distinguish EG from controls and EC from controls. We will then correlate the pattern of gene expression in each disease with tissue eosinophil level for each disease. Furthermore, we will use the histology scoring tools described in Aim 1 to assess the correlation of dysregulated genes and other EoE-, EG-, and EC-related tissue features. During this process, the stringency levels (such as FDR, fold change, P value, etc.) will be interactively adjusted to yield a balance between gene of interest (GOI) pool size and positive prediction. The final leads selection should also be performed in the light of a comprehensive pathway analysis and principle component analysis to guarantee multiple biological processes coverage and minimal redundancy. The resulting GOI pool will be subsequently validated by qPCR and/or protein detection, at least for some of the major GOIs. Based on the identified disease specific genes, and those that track with specific disease characteristics such as tissue levels of eosinophils, mast cells, remodeling, mucus, and cellular hyperplasia, we will embed a set of diagnostic genes into a PCR-based high throughput fluid card, as we recently reported for the development of the EoE Diagnostic Panel (EDP)⁷. An EG diagnostic panel (EG-DP) and EC diagnostic panel (EC-DP) has potential to transform the field as it has potential for rapid, sensitive, specific diagnosis, and can provide information not readily apparent on initial microscopic analysis, as reported for the EoE-DP. It is noteworthy to point out that this potentially transformative undertaking could be scaled for general usage in the field.

Specific Aim 2: Secondary Objective- Determine if specific transcripts within the EoE, EG and EC DPs are reflective of disease activity as determined by COMs. In this aim, we hypothesize that specific genes will correlate with and reflect EoE, EG, and EC disease activity as assessed by the COMs described in Aim 1. We will compare the transcriptomes to COMs to determine which genes best correlate with specific clinical outcomes; this will provide insight into potential pathogenic etiology of specific clinical manifestations and has the potential to predict clinical phenotypes. Preliminary studies by [name] and colleagues have interrogated the EoE-DP for its association with PEESV2.0 questions. In particular, each domain of the PEESV2.0 was correlated with the full set of genes in the EDP, using a cohort of 44 EoE patients with variable levels of esophageal eosinophils. This investigation has shown that the dysphagia domain correlated with a subset of genes. In particular, among the subset of genes were eosinophil associated genes (Charcot Leyden Crystal [CLC] and IL5Ra) and mast cell genes (carboxypeptidase A3 [CPA3]), which achieved statistically significant association. This important and potentially paradigm shifting preliminary finding highlights the proof of concept that gene expression can reflect clinical symptoms and demonstrates the ways in which we will dissect meaningful molecular-clinical data. We are well positioned to employ this innovative approach in our study since we have ready access to tissue specimens and the capabilities to perform molecular analysis, and related bioinformatics processing. Using unsupervised machine learning algorithms, we will determine whether patient samples can be accurately classified according to diagnosis based on their specific gene expression signatures. Signatures will be analyzed using a suite of gene set enrichment programs to identify metabolic pathways and/or gene networks that are enriched in these 3 rare diseases. These studies will provide preliminary data for more detailed studies focused on follow-up validation studies which will likely include studies of identified candidates as potential biomarkers of EoE, EG and EC. If our hypotheses are proven to be correct, they have potential to transform this field as we will test a number of subsequent hypotheses including 1) EoE, EG and EC are characterized by Th2 immune profiles; 2) EG and EC transcriptomes will be different than that from normal controls and 3) specific elements of the EoE, EG and EC transcriptomes will correlate with eosinophil levels (and possibly other features of inflammation). In essence, identification of the DP for each of these diseases has potential to improve monitoring of patients during therapeutic intervention and identify molecular markers with therapeutic significance.

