4.2.2 Secondary Endpoints

Specific Aim 1

- To determine whether COMs change during standard of care treatment
- To determine whether other histological features of eosinophilic inflammation are associated with peak eosinophil counts
- To define the basic clinical and laboratory features of EG and EC.

Specific Aim 2

- To determine if specific transcripts within the EoE, EG and EC DPs are reflective of disease activity as determined by COMS.
- To compare the transcriptomes to COMs to determine which genes best correlate with specific clinical outcomes
- To determine whether patient biopsy samples can be accurately classified according to diagnosis based on their specific gene expression signatures.

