AIM 2: Data analysis and statistical methods for EG and EC will be accomplished as previously reported for EoE^{26, 36}. In brief, individual array quality analyses, normalization, referencing, detection of differences at the exon level, and hierarchical and other clustering approaches are carried out using BioConductor, R, and GeneSpring version v7.3.1 (Agilent, Santa Clara, CA) software as detailed previously²⁶. To determine whether GOIs are also associated with tissue eosinophilia and COMs, we will use either Pearson or Spearman correlations for quantitative variables depending on the variable's distributional properties. Dichotomous outcomes t-tests or Mann-Whitney U will be used for comparisons. To determine the appropriate number of individuals (power), we used MD Anderson's Sample Size for Microarray Experiments. Assuming 30,000 genes and that some genes analyzed will not reach minimal expression levels, a sample size of 20 per group will yield 80% power to detect at least 2-fold differences with no more than 10 false positives. Given the exploratory nature of this Aim, we feel that this sample size appropriately balances statistical power with the currently available resources. Of note, depending upon the findings, results will be validated with qPCR and replication could be performed using additional resources available to CEGIR.

13 Quality Control and Quality Assurance

Training of observational study staff will be conducted by representatives of the DMCC and NIAID prior to beginning recruitment. All staff members will be required to complete certification and quality control in all applicable procedures as outlined in the MOO. The site principal investigators and coordinator(s) will be responsible for ensuring that all procedures are performed according to the protocol. Periodic reviews of procedures will be conducted by the coordinator or other trained personnel according to an individual schedule for each staff member, which is based on the activities he/she is responsible for conducting. Details of the quality control plan, including certifications and quality control of study procedures, are provided in the MOO.

14 Ethics/Protection of Human Subjects

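### The Aim 2 gene-symptom correlations leave out the eosinophil count from the same endoscopy, so they cannot separate added molecular information from a restated count

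*Protocol*

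**What the plan says.** Protocol section 12.5 (Aim 2) names the method: "To determine whether GOIs are also associated with tissue eosinophilia and COMs, we will use either Pearson or Spearman correlations for quantitative variables". Eosinophilia and COMs are two separate pairwise targets, and the count does not enter the gene-COM test.

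The purpose is in section 4.1 (Aim 2, secondary objective): "We will compare the transcriptomes to COMs to determine which genes best correlate with specific clinical outcomes". The same section says that this will shed light on the causes of particular clinical manifestations. Section 4.2.2 repeats the comparison as a secondary endpoint. The supporting pilot correlated PEESS domains with panel genes "using a cohort of 44 EoE patients with variable levels of esophageal eosinophils"; in the result, "among the subset of genes were eosinophil associated genes (Charcot Leyden Crystal [CLC] and IL5Ra) and mast cell genes", the mast-cell gene being CPA3.

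On choosing panel genes, section 4.1 (Aim 2, primary objective) includes "those that track with specific disease characteristics such as tissue levels of eosinophils". Of the EG and EC panels it says that they "can provide information not readily apparent on initial microscopic analysis, as reported for the EoE-DP".

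The only adjustment wording for transcripts is in section 4.2.3, which names age, gender and unspecified other parameters. The Aim 1 regression in section 12.5 relates each COM to the peak count and has no gene term.

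**The concern.** The protocol's hypotheses form a triangle. Section 3.1 expects COMs to correlate with mucosal eosinophilia. Sections 3.1 and 4.1 expect transcripts to correlate with eosinophil levels. Section 4.1 also picks panel genes partly because they follow eosinophil level. If the first two links hold, the third, gene with COM, follows even for a gene that carries no symptom information of its own.

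The planned test looks only at that third link. A positive result fits two explanations: the gene says something about symptoms that the count does not, or it is another reading of the count. The pilot has the same design, with varying eosinophil levels and eosinophil-associated genes among those significant.

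At stake is how the results are read: whether a listed gene points to a mechanism, and whether a panel tells the clinician more than the microscope. Section 12.3 hopes to find variables for a composite score, where redundancy with a count already in hand matters directly.

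**Working it through.** **Inputs from the protocol**
- Aim 2 sample: 20 per disease group, active and untreated (sections 4.2.3 and 5.5). Pilot: 44 (section 4.1).
- Genes: 30,000 with at most 10 false positives (section 12.5), so a per-gene level of 10/30,000 = 0.00033.

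**Assumed, because the protocol gives no values**
- Gene-count correlation 0.8 to 0.9; COM-count correlation 0.2 to 0.4.

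**1. The plan's own figure.** The stated 20 per group is for 2-fold differences between groups at 80% power. No SD is given, so it cannot be confirmed. A two-sided t-test at 0.00033 on the log2 scale reaches 80% power if the SD is about 0.65. The figure is attainable, but it concerns group differences and says nothing about gene-COM correlations.

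**2. Correlation implied when the gene adds nothing.** With a true partial correlation of zero given the count,

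r(gene, COM) = r(gene, count) × r(COM, count).

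Low end: 0.8 × 0.2 = 0.16. Middle: 0.9 × 0.3 = 0.27. High end: 0.9 × 0.4 = 0.36.

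**3. Chance of nominal significance.** By Fisher z, the test statistic has mean √(n − 3) × atanh(r) and SD 1, two-sided alpha 0.05. At n = 20, √17 = 4.12.

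| r(gene, COM) | atanh | mean, n = 20 | significant, n = 20 | significant, n = 44 |
|---|---|---|---|---|
| 0.16 | 0.161 | 0.67 | 10% | 18% |
| 0.27 | 0.277 | 1.14 | 21% | 43% |
| 0.36 | 0.377 | 1.55 | 34% | 67% |

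At a level of 0.00033 and n = 20 the range is about 0.2% to 2%. With a COM-count correlation of only 0.14 (the EoE detectable value in section 12.4) it is about 8% at n = 20 and alpha 0.05.

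**4. Same gene, count partialled out.** In simulations of 20,000 samples per setting (n = 20 and 44; gene-count 0.7 to 0.9; COM-count 0.26 to 0.5), the partial correlation was significant in about 5% throughout, as it should be when nothing is added.

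**5. Cost in sensitivity.** Detectable r at 80% power is tanh[(1.96 + 0.84)/√(n − 3 − k)], with k covariates. At n = 20: k = 0 gives tanh(0.679) = 0.59; k = 1 gives tanh(0.700) = 0.60.

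**6. Limit of the adjustment.** Suppose gene, measured count and COM all reflect a latent eosinophil burden, with assumed correlations 0.9, 0.7 and 0.4. Then gene-COM = 0.36, gene-count = 0.63, count-COM = 0.28, and the partial correlation is (0.36 − 0.63 × 0.28) / √[(1 − 0.63²)(1 − 0.28²)] = 0.25. That is significant in 17% of analyses at n = 20. Error in the count therefore leaves some overlap.

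**The case against.** The strongest reply is that Aim 2 does not ask this question. Section 4.2.2 asks whether transcripts reflect disease activity and which genes correlate best with outcomes; a simple correlation answers that. Added value over the count is neither an objective nor an endpoint. This stands, and it is why the simple correlation should stay and genes should not be ranked on the partial one alone. It does not cover the pathogenic reading or the expectation about microscopy, both of which section 4.1 states.

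A reader might infer that eosinophil transcripts only restate the count. The protocol does not show this: it gives no gene-count or COM-count correlation, and the pilot result includes a mast-cell gene. A reader might also call the rates above false signals. They are not: in the assumed model the marginal correlation (0.27 in the middle case) is real, and what fails is its interpretation as added information.

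The restriction to active, untreated disease may narrow the range of counts and weaken the effect compared with the pilot. Section 4.1 also asks for pathway and principal-component analysis to limit redundancy among selected genes, which works against a panel dominated by eosinophil markers.

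Adjustment is imperfect too. The peak count comes from one high-power field (section 4.2.1), while RNA may come from separate research biopsies. The count may also lie on the path from gene to symptom.

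Finally, Aim 2 is labelled exploratory, the unnamed other parameters in section 4.2.3 could include the count, and a statistical analysis plan may add it. But section 12.5 does name the method, and as named it leaves the count out.

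**Conclusion.** The point holds for the gene-COM part of Aim 2. As specified, that analysis cannot tell molecular information beyond the count from a restatement of it, so a significant correlation does not by itself support a pathogenic interpretation or an advantage over microscopy. This follows from the protocol's own hypotheses and needs no assumed figure.

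The size does need assumptions. Over the ranges above it is 10% to 34% per gene at the planned n = 20 and alpha 0.05, and about 0.2% to 2% at the 10/30,000 level.

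It would go too far to conclude that Aim 2 as a whole cannot show added value. Disease-control profiles, correlation with other tissue features and classification by diagnosis do not rest on this test.

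**What to change.** In section 12.5 (Aim 2), keep the simple correlation for the stated endpoint. For each gene-COM pair, add the partial (rank) correlation, or the gain in R², given the peak eosinophil count from the same endoscopy. Limit any claim of information beyond the count to genes that keep an association after this adjustment.

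State three limits with it:
- A partial association that vanishes does not separate a marker of eosinophil number from a gene acting through eosinophils.
- Error in the count leaves residual overlap, so a surviving association is not proof of added information.
- At n = 20 only partial correlations of about 0.6 are detectable with 80% power.

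The cost is one degree of freedom and a little extra analysis. The count is already collected, and the detectable correlation at n = 20 moves only from 0.59 to 0.60.
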